If the patient does not agree to return for all remaining scheduled visits, the patient should be encouraged to return at least for an early EoT (eEOT) Visit within 7 days of the last dose of trial medication, for the regularly scheduled Visit 10 and EOS. If EOS visit (early drug discontinuation date + 28 +2 days) can be completed prior to the date of the planned Visit 10, no additional FUP Visit may be needed. However, end of study participation (EOS) must be completed.

Section 6.2.3

If the last day of trial drug intake is different from the day prior to the EOT visit, the date of the last day of trial drug intake will be used for calculation of the EOS visit date.

Was changed to:

If the last day of trial drug intake is different from the day prior to the EOT visit, the date of the last day of trial drug intake will be used for calculation of the FUP/EOS visit date.

Flow Chart 1&2

The following was added to V11 visit description:
Follow-up Visit (FUP) /

Flow Chart 1, Footnote**
After this early EOT visit, patients should be followed up according to the regularly scheduled visit for both clinic and phone visits until Visit 10 and should be encouraged to complete the FUP Visit 28+2 days after the drug discontinuation date

All procedures should be completed, with the exception of trial drug procedures and PK collections. If a regular planned visit is completed prior to the initially planned Visit10 (early drug discontinuation date + 28+2 days),

Page 128 of 148

Proprietary confidential information © 2023 Boehringer Ingelheim International GmbH or one or more of its affiliated companies

no additional FUP is needed. However, end of study participation must be completed.

If the patient does not agree to return for all remaining scheduled visits, the patient should be encouraged to return at least for an early EoT (eEOT) Visit within 7 days of the last dose of trial medication, for the regularly scheduled Visit 10 and FUP. If FUP visit (early drug discontinuation date + 28 +2 days) can be completed prior to the date of the planned Visit 10, no additional FUP is needed. However, end of study participation must be completed.

Was changed to:

After this early EOT visit, patients should be followed up according to the regularly scheduled visit for both clinic and phone visits including Visit 10 and should be encouraged to complete the FUP Visit 28+2 days after the drug discontinuation date

All procedures should be completed, with the exception of trial drug procedures and PK collections. If a regular planned visit is completed prior to the initially planned Visit10 (early drug discontinuation date + 28+2 days), no additional FUP Visit may be needed. However, end of study participation (EOS) must be completed.

If the patient does not agree to return for all remaining scheduled visits, the patient should be encouraged to return at least for an early EoT (eEOT) Visit within 7 days of the last dose of trial medication, for the regularly scheduled Visit 10 and FUP. If FUP visit (early drug discontinuation date + 28 +2 days) can be completed prior to the date of the planned Visit 10, no additional FUP Visit may be needed. However, end of study participation (EOS) must be completed.

c34993667-05 Clinical Trial Protocol Page 129 of 148

Proprietary confidential information © 2023 Boehringer Ingelheim International GmbH or one or more of its affiliated companies

Rationale for change	Clarification
Sections to be changed	Section 4.2.2.1
Description of change	For patients who are not on current treatment with benzodiazepine (including Z-drugs) or non-benzodiazepine hypnotics at the time of screening, the protocol will allow concomitant use of non-benzodiazepine-, non-Z-drug hypnotics during the trial at dose equivalent to ≤ 1.0 mg lorazepam per day.
	Was changed to:
	For patients who are not on current treatment with benzodiazepine (including Z-drugs) or non-benzodiazepine hypnotics at the time of screening, the protocol will allow concomitant use of non-benzodiazepine-, non-Z-drug hypnotics at lowest dose of the compound as noted in the Summary of Product Characteristic (or SmPC) during the trial.
Rationale for change	Removal of lorazepam dose equivalent as this is not applicable in this trial for concomitant use started during the trial.
Sections to be changed	Table 5.4.3:1
Description of change	Hepatitis C Vaccine
	Was changed to:
	Hepatitis C Virus
Rationale for change	Correction of term.
Sections to be changed	Section 5.4.5.1

c34993667-05 Clinical Trial Protocol Page 130 of 148

Proprietary confidential information © 2023 Boehringer Ingelheim International GmbH or one or more of its affiliated companies

Description of change	For 'Self-injurious behavior, no suicidal intent' (Type 11) standard AE / SAE reporting rules are to be applied.
	Was changed to: For 'Self-injurious behavior, no suicidal intent' standard AE / SAE reporting rules are to be applied.
	The following text was added to the last paragraph: Please note, that adverse event reports, that get coded to terms like suicidal depression,
	suicidal ideation, suicidal threat or similar, are on the "Always serious AE List" and therefore must be reported as SAEs (refer to section 5.4.6.1.3).
Rationale for change	Reference to "Always serious adverse event list" added for clarification.
Sections to be changed	Section 6.2
Description of change	The following text was added: The CAPS-5 rater should review the LEC and Extended Criterion A upon completion by the patient before the patient completes the PCL-5 to identify the index traumatic event to be referred to during patient's PCL-5 completion and the CAPS-5 administration. It is essential that the referenced index traumatic event is consistent for PCL-5 and CAPS-5 assessments. CTQ was added to listed assessments.
Rationale for change	Clarification of process.
Amazinia ivi change	Ciaminamon of process.
Sections to be changed	Section 6.2.1

c34993667-05 Clinical Trial Protocol Page 131 of 148

Proprietary confidential information © 2023 Boehringer Ingelheim International GmbH or one or more of its affiliated companies

Description of change	Concomitant treatments which are allowed or restricted before and during trial participation, including required washout durations, are listed in the ISF. Patients will be instructed to continue allowed/required background medication without changes and to adhere to their administration algorithm. Was changed to: Concomitant treatments which are restricted before and during trial participation, are listed in the ISF. Patients will be instructed to continue allowed background medication without changes and to adhere to their administration algorithm.
Rationale for change	Correction to remove not applicable text.
Sections to be changed	Section 8.1
Description of change	Prior to patient participation in the trial, written informed consent must be obtained from each patient (or the patient's legally accepted representative) according to ICH-GCP and to the regulatory and legal requirements of the participating country. Was changed to:
	Prior to patient participation in the trial, written informed consent must be obtained from each patient according to ICH-GCP and to the regulatory and legal requirements of the participating country.
Rationale for change	Legal accepted representatives are not applicable for this trial.
Sections to be changed	Throughout the document
Description of change	Typos, formatting and duplicate wording corrected and paragraph moved within section
Rationale for change	Administrative changes to increase clarity, quality and readability.

c34993667-05 Clinical Trial Protocol Page 132 of 148

Proprietary confidential information © 2023 Boehringer Ingelheim International GmbH or one or more of its affiliated companies

GLOBAL AMENDMENT 2 11.2

Date of amendment	26 Sep 2022	
EudraCT number/EU number	2021-003154-23	
BI Trial number	1402-0030	
BI Investigational Medicinal Product(s)	BI 1358894	
Title of protocol	A Phase II, 8-week-treatment, multicenter, randomized, double-blind, placebo-controlled, parallel group trial to evaluate the efficacy, tolerability and safety of orally administered BI 1358894 in patients with Post-Traumatic Stress Disorder (PTSD)	
Global Amendment due to urgent safety reasons	N/A	
Global Amendment	2	
Section to be changed	CLINICAL TRIAL PROTOCOL SYNOPSIS	
Description of change	Women of childbearing potential (WOCBP) able and willing to use two methods of contraception, Was changed to:	
	• Women of childbearing potential (WOCBP) able and willing to use two methods of contraception, confirmed by the investigator,	
Rationale for change	To follow an FDA request and to ensure that the investigator confirms the contraception requirement with the patient.	
Section to be changed	Flow Chart 1 footnote 16	
Description of change	Contraception counseling for WOCB	
	Was changed to:	
	Contraception counseling for WOCB ¹⁶	
	16 This must include confirmation from the patient that she is using required contraception consistently and appropriately. Counseling and contraception confirmation	

c34993667-05 Clinical Trial Protocol Page 133 of 148

Proprietary confidential information © 2023 Boehringer Ingelheim International GmbH or one or more of its affiliated companies

	must be recorded in CRFs Refer to section 4.2.2.3 for more details regarding contraception counseling.
Rationale for change	To follow an FDA request and to reinforce that contraception counseling is done at every visit and documented.
Section to be changed	Section 1.4.2
Description of change	Additionally, investigators must counsel WOCBP with regard to the importance of contraception at all visits as per Flow Chart (including phone visits).
	Was changed to:
	Additionally, investigators must counsel WOCBP with regard to the importance of contraception and confirmation of appropriate contraception use at all visits as per Flow Chart (including phone visits).
Rationale for change	To follow an FDA request and to reinforce that contraception counseling is done at every visit and documented.
Castion to be shanged	Table 1.4.2: 1
Section to be changed Description of change	Embryo-fetal development toxicity
	Section was updated: Investigator must ensure that the patient understands the contraception requirements for the study and must confirm that the patient can
	reliably comply with contraception use during the study. Patients not expected to comply with contraception requirements should not be included in the study.
	Pregnancy testing must be performed at every site visit.
	Investigators must counsel WOCBP with regard to the need for contraception, including confirmation of the use of contraception, at all visits as per Flow Chart 1 (including phone visits).
	Refer to section 4.2.2.3 for more details regarding contraception counseling.

c34993667-05 Clinical Trial Protocol Page 134 of 148

Proprietary confidential information © 2023 Boehringer Ingelheim International GmbH or one or more of its affiliated companies

Rationale for change	To follow an FDA request and to reinforce that contraception counseling is done at every visit and documented.	
Castian to be abanged	Section 3.3.2	
Description of change	7. Women who are of child-bearing potential (WOCBP) ¹ must be able and willing to use two methods of contraception which include one highly effective method of birth control per ICH M3 (R2) that result in a low failure rate of less than 1%, plus one additional barrier method.	
	7. Women who are of child-bearing potential (WOCBP) ¹ must be able and willing to use two methods of contraception, as confirmed by the investigator, which include one highly effective method of birth control per ICH M3 (R2) that result in a low failure rate of less than 1%, plus one additional barrier method.	
Rationale for change	To follow an FDA request and to ensure that the investigator confirms the contraception requirement with the patient.	
Section to be changed	4.2.2.3	
Description of change	Section was updated: Counseling about the importance of having birth control measures in place will be performed at study entry visit (during consenting process), informing women about the risk of medication-induced births defects when exposed to potentially teratogenic medication. Investigator must ensure that the patient understands the contraception requirements for the study and must confirm that the patient can reliably comply with contraception use during the study. Patients not expected to comply with contraception requirements should not be included in the study.	

c34993667-05 Clinical Trial Protocol Page 135 of 148

Proprietary confidential information © 2023 Boehringer Ingelheim International GmbH or one or more of its affiliated companies

	The importance of continuing with their chosen forms of birth control during study conduct will be emphasized to mitigate this risk and it must be reiterated at all visits as per Flow Chart 1 including phone visits). This must include confirmation from the patient that she is using required contraception consistently and appropriately. If contraceptive protection cannot be confirmed, as judged by the investigator, the patient must be discontinued from the study drug. Study drug can be restarted only when contraception is used again, and sufficient protection is reached. Counseling and contraception confirmation must be recorded in CRFs.
Rationale for change	To follow an FDA request and to reinforce that contraception counseling is done at every visit and documented. Also to provide guidance for investigators on contraception rules.

c34993667-05 Clinical Trial Protocol Page 136 of 148

Proprietary confidential information © 2023 Boehringer Ingelheim International GmbH or one or more of its affiliated companies

Sections to be changed	Flow Chart 1 & 2
Description of change	Description
	-28 days to 0 V1A anytime up to day -7
	Was changed to:
	-28 days V1A anytime up to 8 days before V2
Rationale for change	Clarification of screening period definition.
Sections to be changed	Section 5.8.1, Figure 5.8.1.1:1

c34993667-05 Clinical Trial Protocol Page 137 of 148

Proprietary confidential information © 2023 Boehringer Ingelheim International GmbH or one or more of its affiliated companies

Description of change	Section 5.8.1	
•	A daily/weekly diary design beginning 7 days prior to the randomization visit and then over	
	the 8-week treatment period will be used.	
	Was changed to:	
	A daily/weekly diary design for 7 days prior to the randomization visit and then over	
	the 8-week treatment period will be used.	
	Figure 5.8.1.1:1	
	Visit 1A	
	up to day -7	
	Was changed to:	
	Visit 1A min. 8 days prior V2	
	56 days	
	Day 2 (the day after V2) to Day 56 (day before V10)	
	Was changed to:	
	55 days (+2)	
	Day 2 (the day after V2) to Day 56 (+2) (day before V10)	
Rationale for change	Clarification of assessment period definition. Figure 5.8.1.1.:1 was updated to be aligned screening period clarification and EcMA PANAS daily was corrected.	
Sections to be changed	Footnotes Flow Chart 1 & 2, section 6.2, section 6.2.2	

Page 138 of 148

Proprietary confidential information © 2023 Boehringer Ingelheim International GmbH or one or more of its affiliated companies

Description of change

Footnote to Flow Chart 1 & 2:

At the screening visit, all clinical examinations and assessments as per Flow Chart 1 will be performed first, except for the blood draws, followed by PCL-5,CAPS-5 and MINI, followed by the other scale administrations, listed in Flow Chart 2. The order of assessments is described in detail in section 6.2.

For all further clinical visits, scale administrations should be done first, followed by the clinical examinations and assessments (Flow Chart 1) Please refer to section 6.2 for further details.

Was changed to:

At the screening visit, all clinical examinations and procedures as per Flow Chart 1 should be performed first, followed by PCL-5 (version comprising LEC, Extended Criterion A and PCL5),CAPS-5 and MINI, followed by the other clinical outcome assessments, listed in Flow Chart 2. Blood draws are preferably done after clinical outcome assessments. The order of assessments and procedures is described in detail in section 6.2.

For all further clinical visits, please refer to section 6.2.2 for details on order of assessments and procedures.

The following text was removed:

All baseline assessments must be performed prior to the first intake of the trial medication.

Section 6.2:

Order of Assessments at Screening Visit
At the screening visit, all clinical examinations and assessment (Flow Chart 1) should be performed first except for the blood draws, followed by the clinical outcome measurements (Flow Chart 2) in the following order.

Boehringer Ingelheim BI Trial No.: 1402-0030

09 Jun 2023

Page 139 of 148

c34993667-05 Clinical Trial Protocol Page

The following assessments 1. to 5. must be in the specific order:

1. Life Events Checklist (as part of PCL-5)

2. Extended Criterion A (as part of PCL-5)

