- 5 Patients duplicate check is a mandatory process, local amendments will be prepared as applicable. Registration of patient in the during the Screening Visit; no further action for the site staff during the course of the study.
- 6 Demographics in the eCRF will include questions on potential disability payments related to PTSD
- 7 The patient will be asked to evaluate the impact of COVID-19 pandemic restrictions. Please refer to section 6.2.2. for detailed information.
- 8 For WOCBP, a serum pregnancy test will be performed at screening and urine pregnancy tests at all clinic visits beginning with V1A. If a urine pregnancy test is positive, a serum test needs to be performed for confirmation.
- 9 Infection testing during V1 for hepatitis B and hepatitis C.
- 10 Patients will bring trial medication (used/unused blister and covering packages) to site visits for compliance check (V4,V6,V8, EOT/eEOT) and for resupply (V4,V6,V8). Patients have to take the IMP at the trial site at all treatment visits (except V10/EOT) to allow adequate sampling of pharmacokinetic samples. Last regular intake of the trial drug is the day before EOT

Boehringer Ingelheim BI Trial No.: 1402-0030 c34993667-05 Clinical Trial Protocol

09 Jun 2023

Page 11 of 148

Proprietary confidential information © 2023 Boehringer Ingelheim International GmbH or one or more of its affiliated companies

- 13 One sample for remains valid will be taken, preferably at Visit 2. However, collection at later visits is permitted as long as the informed consent
- 14 After the EoStudy visit (= individual patient's end of the trial) the investigator should report only any cancers of new histology and exacerbations of existing cancer, trial treatment related SAEs and trial treatment related AESIs of which the investigator may become aware of and only via the BI SAE form, please see section 5.4.6.2.2.
- 15 Substance in the eCRF is defined as: caffeine, nicotine and alcohol.
- 16 This must include confirmation from the patient that she is using required contraception consistently and appropriately. Counseling and contraception confirmation must be recorded in CRFs Refer to section 4.2.2.3 for more details regarding contraception counseling.

For potential modifications of trial conduct in case of restrictions due to COVID-19, please refer to sections 4.1.4, 6.1, 8.1 and 10.3

Page 12 of 148

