1.4.1 Benefits

This is an experimental drug at an early stage of testing and therefore an individual benefit cannot be guaranteed. Potential efficacy has been demonstrated in pre-clinical and PoCP data.

1.4.2 **Risks**

In a comprehensive package of safety pharmacology, genetic toxicology, general toxicology, and nonclinical studies, BI 1358894 was demonstrated to be safe in humans for up to 13 weeks. Based on the mode of action, the pharmacological target, non-clinical toxicology data and clinical data, BI 1358894 is not considered a high-risk compound for clinical studies. As in other clinical trials, trial patients are exposed to the risks related to the exposure to the trial medication and to the risks of the trial procedures.

In one completed pivotal embryo-fetal development study in Goettingen minipigs, embryo-fetal development toxicity was identified (decreased number of implantations, increased number of early resorptions, decreased fetal weight, skeletal malformations) at relevant human exposure levels. Maternal toxicity was not seen at human relevant doses. The NOAEL shows that the findings are relevant for the maximum dose (125 mg once daily) tested in the ongoing clinical trials.

Therefore, a risk for teratogenicity in humans cannot be excluded. To mitigate this risk, women of childbearing potential (WOCBP) who are heterosexually active must agree and adhere to contraceptive measures consisting of one highly effective method of birth control per ICH M3 (R2) that results in a low failure rate of less than 1% plus one additional barrier method during the treatment and follow-up period of the trial. Pregnancy testing has to be performed at every site visit. Additionally, investigators must counsel WOCBP with regard to the importance of contraception and confirmation of appropriate contraception use at all visits as per Flow Chart 1 (including phone visits).

While there are no precedent clinical data implicating association between TRPC4/5 antagonism and Suicidal Ideation and Behavior (SIB), in the interest of ensuring patient safety, trial patients will be proactively screened and monitored throughout the trial for SIB in accordance with available regulatory guidance.

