Dose group	Number of tablets to be taken daily – in the morning 🌣			morning 🌣
Placebo	0	0	1	2
125 mg	1	2	0	0

During the COVID-19 pandemic, there might be situations that would not allow a patient to come to the site for the study visit. If the investigator judges it as acceptable and safe to continue trial medication, trial medication might be shipped from the site to the patient (for more details see section 6.1 and 10.3).

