4.2.2.3 Contraception requirements

Women of childbearing potential (WOCBP - for the definition please refer to section 3.3.2) must use two methods of contraception, which include one highly effective methods of birth control per ICH M3 (R2) that result in a low failure rate of less than 1%, plus one additional barrier method. Contraception must be used during the treatment and follow-up period.

Women of child-bearing potential must agree to periodic pregnancy testing during participation in the trial. If a urine pregnancy test is positive, a serum test needs to be performed for confirmation.

Counseling about the importance of having birth control measures in place will be performed at study entry visit (during consenting process), informing women about the risk of medication-induced births defects when exposed to potentially teratogenic medication. Investigator must ensure that the patient understands the contraception requirements for the study and must confirm that the patient can reliably comply with contraception use during the study. Patients not expected to comply with contraception requirements should not be included in the study.

The importance of continuing with their chosen forms of birth control during study conduct will be emphasized to mitigate this risk and it must be reiterated at all visits as per Flow Chart 1 (including phone visits). This must include confirmation from the patient that she is using required contraception consistently and appropriately. If contraceptive protection cannot be confirmed, as judged by the investigator, the patient must be discontinued from the study drug. Study drug can be restarted only when contraception is used again, and sufficient protection is reached. Counseling and contraception confirmation must be recorded in CRFs.

Page 60 of 148

Proprietary confidential information © 2023 Boehringer Ingelheim International GmbH or one or more of its affiliated companies

Acceptable forms of contraception are:

One of the highly effective methods of birth control per ICH M3 (R2) that result in a low failure rate of less than 1%:

- Use of hormonal methods of contraception associated with inhibition of ovulation
 - o a. combined (estrogen and progestogen containing) hormonal contraception:
 - oral
 - intravaginal
 - transdermal
 - o b. progestogen-only hormonal contraception:
 - oral
 - injectable
 - Implantable

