Randomization should not be performed in case of a positive urine pregnancy test (to be completed locally on-site using kits provided by central lab). In this case, a serum pregnancy test will be performed by the central lab for confirmation.

Upon randomization via the IRT, medication kit will be dispensed. Trial medication is
administered after
The first dose should be taken at the clinic after all Visit 2 assessments and procedures are
completed, except for remaining patient reported clinical outcome assessments including
optional speech recordings as described above, and followed by

. Samples for optional plasma/serum and DNA biobanking will be collected if Informed Consent is provided. A sample for DNA biobanking is preferentially collected at Visit 2 but can be collected at another time point thereafter.

Trial drug kits will be dispensed for home administration.

Visit 4, Visit 6, Visit 8

Patients should not take trial medication before coming to the clinic. This is because patients will be dosed at the clinic. When applicable, dosing should occur after safety lab samples and samples are taken if applicable (please refer to Appendix 10.2).

Pandemic restrictions

At Visit 6, the patient will be presented with questions to evaluate the impact of COVID-19 pandemic restrictions. The assessment period will be aligned with the CAPS-5 recall period (i.e. past week).

Phone visits

Visit 3, Visit 5, Visit 7 and Visit 9 will be conducted by phone or by video call, if in line with local regulation.

At Visit 9, patients will be instructed to take the last dose of study medication on **the day before** the EOT visit.

Page 93 of 148

Proprietary confidential information © 2023 Boehringer Ingelheim International GmbH or one or more of its affiliated companies

Visit 10 / End of Treatment (EOT) Visit

For patients completing the 8-week treatment, this visit will be EOT visit. For patients who discontinue study treatment prematurely and continue with study visits, this visit at Week 8 will be their Visit 10.

EOT visit represents the end of the treatment period. Last study drug administration will be on the day before EOT visit. The overall duration of the anticipated treatment period (Randomization to EOT) should not be less than 56 days; therefore the EOT visit is scheduled at Day 57 with a visit window of up to +2 days.

Patients prematurely discontinuing study drug

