10.3 POTENTIAL MODIFICATION OF TRIAL CONDUCT IN CASE OF RESTRICTIONS DUE TO COVID-19

As mentioned in section 6.1, in case of any restrictions during the COVID-19 pandemic, study conduct may need to be adjusted. The following contingency measures have been introduced to ensure patient safety and appropriate trial continuation based on a thorough benefit-risk assessment (see section 1.4.2).

Under these circumstances, the below modifications can be considered.

Safety lab, other laboratory tests

If taking blood samples for central lab is not possible, blood analysis for safety lab can be done in a local lab. The results of the lab tests are to be reported and transferred to the investigator, who has to ensure medical review and proper documentation.

Safety lab parameters should at least include liver enzymes and Bilirubin, haematology including differential test, blood glucose, sodium, potassium, creatinine, urea (BUN) and eGFR. It is important that always the reference values of the local lab are also provided.

Dispensation of Trial medication (IMP)

If a participant is not able to come to visit 4, visit 6 or visit 8 as planned and the investigator considers it acceptable and save for participant to continue with IMP, IMP can be shipped from site directly to the participant (if legally acceptable according to local regulations).

If home visits by trial staff members or e.g. "Home Healthcare Nurse" are possible, further assessments can be done like e.g. vital signs, blood draw for safety lab and biomarkers as well as collection of urine samples to be sent to central lab, or compliance check.

c34993667-05 Clinical Trial Protocol Page 115 of 148

Proprietary confidential information © 2023 Boehringer Ingelheim International GmbH or one or more of its affiliated companies

DESCRIPTION OF GLOBAL AMENDMENT(S) 11.

11.1 **GLOBAL AMENDMENT 1**

Date of amendment	03 May 2022
EudraCT number/EU number	2021-003154-23
BI Trial number	1402-0030
BI Investigational Medicinal Product(s)	BI 1358894
Title of protocol	A Phase II, 8-week-treatment, multicenter, randomized, double-blind, placebo-controlled, parallel group trial to evaluate the efficacy, tolerability and safety of orally administered BI 1358894 in patients with Post-Traumatic Stress Disorder (PTSD)
Global Amendment due to urgent safety reasons	X
Global Amendment	1
Sections to be changed	Flow Chart 1; Flow Chart 1 footnote 8; Table 5.4.3:1

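### Protocol 10.3 and 4.1.4 let drug be shipped for a missed Visit 4, 6 or 8 without the urine pregnancy test due at that visit, so testing can lapse while dosing continues

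*Protocol*

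**What the plan says.** **Scheduled testing.** Flow Chart 1 marks a pregnancy test at Visits 1, 1A, 2, 4, 6, 8 and 10, at early end of treatment and at follow-up. Footnote 8 specifies a serum test at screening, then "urine pregnancy tests at all clinic visits beginning with V1A", with serum confirmation of any positive urine result. Section 1.4.2 states: "Pregnancy testing has to be performed at every site visit". Section 1.4.3 and Table 1.4.2:1 repeat that rule. Section 4.2.2.3 is looser: "Women of child-bearing potential must agree to periodic pregnancy testing during participation in the trial".

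**The test as a gate.** At Visit 2, section 6.2.2 says: "Randomization should not be performed in case of a positive urine pregnancy test".

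**When a visit cannot be attended.** Section 4.1.4 provides: "If the investigator judges it as acceptable and safe to continue trial medication, trial medication might be shipped from the site to the patient". Section 10.3 names Visits 4, 6 and 8, repeats the investigator's judgement and adds local law: "IMP can be shipped from site directly to the participant (if legally acceptable according to local regulations". If home visits are possible, "further assessments can be done like e.g. vital signs, blood draw for safety lab and biomarkers as well as collection of urine samples", with the urine going to the central laboratory. The minimum parameter list for local laboratories in 10.3 and 5.4.3 does not contain hCG.

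**Contraception.** Section 4.2.2.3 requires counselling and confirmation of use at the visits marked in Flow Chart 1, phone visits included, and adds: "If contraceptive protection cannot be confirmed, as judged by the investigator, the patient must be discontinued from the study drug".

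**The concern.** The visits at which drug may be replaced by a shipment are exactly the visits that carry the on-treatment pregnancy tests. Shipment depends on the investigator's judgement and, in 10.3, on local law. It does not depend on a test result. A site that follows 10.3 as written can resupply a woman of childbearing potential without testing her.

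The protocol's own risk assessment makes this matter:

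- Section 1.4.2 does not exclude teratogenicity in humans and calls the minipig findings relevant at 125 mg.
- Section 1.2 gives embryo-fetal safety margins at that dose of 1.4 (Cmax) and 1.6 (AUC).
- Section 1.4.3 counts the pregnancy-risk measures, testing among them, when it concludes that benefit outweighs risk.

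Phone confirmation covers what a woman reports about contraception. It does not detect a pregnancy. The rule in 3.3.4.1 to stop drug for pregnancy works only once the pregnancy is known. Because the residual effect period is 28 days, stopping after late detection does not end exposure at once.

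The visible entries for Global Amendments 1 and 2, which strengthened pregnancy testing and contraception confirmation, list no matching change to 4.1.4 or 10.3. This looks like an oversight and not a decision.

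**Working it through.** There is no planned figure to reproduce, so the check has two parts: the wording, then the test interval that the wording permits.

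**Wording, rule by rule**

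| Place | Tied to | Makes shipment depend on a test? |
|---|---|---|
| 1.4.2, 1.4.3, Table 1.4.2:1 | site visits | No |
| Flow Chart 1 footnote 8, Table 5.4.3:1 | clinic visits | No |
| 4.2.2.3 | unspecified periodic testing | No |
| 4.1.4 | investigator's judgement | No |
| 10.3, shipment | investigator's judgement and local law | No |
| 10.3, local laboratory minimum | list without hCG | No |
| 10.3, home visit | optional; pregnancy test not named | No |
| 6.2.2, Visit 2 | randomization | Not applicable (gate on randomization) |

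The shipment sentences in 4.1.4 and 10.3 are complete, so redaction does not explain the gap.

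**Interval between tests**

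Inputs from Flow Chart 1, as study days with their windows: Visit 2 = 1; Visit 4 = 15 (13 to 17); Visit 6 = 29 (27 to 31); Visit 8 = 43 (41 to 45); Visit 10 = 57 (57 to 59).

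Formulas, for consecutive tested visits a and b:

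- nominal = day(b) − day(a)
- shortest = earliest(b) − latest(a)
- longest = latest(b) − earliest(a)

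| Situation | Between tests | Nominal | Shortest | Longest |
|---|---|---|---|---|
| As scheduled | V4 to V6 | 29 − 15 = 14 | 27 − 17 = 10 | 31 − 13 = 18 |
| V4 remote | V2 to V6 | 29 − 1 = 28 | 27 − 1 = 26 | 31 − 1 = 30 |
| V6 remote | V4 to V8 | 43 − 15 = 28 | 41 − 17 = 24 | 45 − 13 = 32 |
| V8 remote | V6 to V10 | 57 − 29 = 28 | 57 − 31 = 26 | 59 − 27 = 32 |
| V4 and V6 remote | V2 to V8 | 43 − 1 = 42 | 41 − 1 = 40 | 45 − 1 = 44 |
| V6 and V8 remote | V4 to V10 | 57 − 15 = 42 | 57 − 17 = 40 | 59 − 13 = 46 |
| V4, V6 and V8 remote | V2 to V10 | 57 − 1 = 56 | 57 − 1 = 56 | 59 − 1 = 58 |

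If Visits 4 and 8 are remote and Visit 6 is attended, the nominal interval is 28 days on each side of Visit 6. The last row of the table is the whole treatment period.

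**Supply already in hand**

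Section 4.1.4 gives two 14-day kits at Visit 2, one of them a reserve: 2 × 14 = 28 days, Days 1 to 28. A woman who misses only Visit 4 can therefore dose up to the day before the nominal Visit 6 with no shipment and no test. A condition placed on shipment alone would miss this case.

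**The case against.** The strongest reply is that silence is not permission. Flow Chart 1 assigns the test by visit number, 6.1 obliges patients to keep to the schedule, and 10.3 lists what may be modified without listing the pregnancy test. The clinic-visit wording in footnote 8 can also be read as a type of visit, because only Visits 3, 5, 7 and 9 are phone visits. On that reading a remote Visit 4, 6 or 8 still owes a test. Shipment is not unconditional either: the investigator must judge it safe, and 10.3 points to the benefit-risk assessment in 1.4.2, where the teratogenicity risk is set out. Section 6 permits documented alternative methods, home visits may collect urine, the local laboratory list is only a minimum, and the Laboratory Manual and Investigator Site File may say more. Two-method contraception, the main safeguard, continues with a stop-drug rule.

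Two narrower points concern the remedy and the mechanism. For Visits 4, 6 and 8 held on site, the protocol states no explicit rule that a negative result must precede dispensing, so a gate on remote resupply is stricter than the written on-site rule. And a missed Visit 4 need not involve a shipment at all.

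Much of this stands. Section 10.3 does not waive the test, the wording is ambiguous, and only testing can lapse, because the contraception checks continue. But no cited provision makes resupply depend on a test or says how a woman who cannot attend is to be tested. The site-visit wording in 1.4.2, 1.4.3 and Table 1.4.2:1 supports the reading that no test is owed. On the gate, the test and the resupply fall at the same visit when it is held on site; remote shipment separates them, and Visit 2 already provides the model. The Visit 4 point is correct and is met by extending the condition to the reserve kit.

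**Conclusion.** The concern holds. Sections 10.3 and 4.1.4 allow dosing to continue remotely without the pregnancy test due at that visit. The test interval can then grow from 14 days to 28, 42 or, at worst, 56 days (58 with the visit window).

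The figures assume that each remote visit passes with no test and that the woman stays on drug. The 56-day case needs all three visits to be remote. The documents state neither how often visits would be remote nor how many women of childbearing potential are expected. With two contraceptive methods required, the number affected is likely small. The issue is confined to COVID-19 restrictions and has no bearing on sample size, power or the efficacy analysis.

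The change should be made because the possible harm is serious, the protocol itself relies on testing to justify the risk, and the remedy is cheap. It need not trigger an amendment of its own.

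**What to change.** Add to 10.3 and 4.1.4 that, for women of childbearing potential, drug is shipped only after two things are documented for that visit: a negative urine pregnancy test (home dipstick kit, home visit or local laboratory) and confirmed contraception. A positive urine result goes to serum confirmation, as footnote 8 already provides. Apply the same condition to starting the reserve kit when Visit 4 is remote. This keeps the interval at the scheduled 14 days, at most 18 with the visit windows.

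The cost is two or three sentences. Amendments need ethics committee and authority approval under 8.1, so the change is best bundled with the next one. Test kits would have to reach patients at home; the protocol describes their use on site only, so this is new logistics. Waiting for a result could delay resupply briefly or cost a few doses. Sending the kit ahead, so that the test falls within the ±2-day window, reduces that risk.
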